2.1.5 Pharmacokinetic endpoints

Pharmacokinetic variables include C_{max} , t_{max} , area under the curve (AUC_{0-last}), clearance (CL), and volume of distribution (Vd).

2.1.6 Efficacy endpoints

The baseline value for efficacy endpoints is the same as the baseline definition in [Section 2.1.1](#).

Efficacy endpoints include the following:

Gross Motor Function Measure-88 and Gross Motor Function Classification System - Expanded and Revised

GMFM-88 was developed specifically to detect quantitative changes in gross motor function. There is no age cut-off for the GMFM-88. The GMFM-88 consists of 88 items organized into 5 dimensions:

- Lying and rolling (17 items)
- Sitting (20 items)
- Crawling and kneeling (14 items)
- Standing (13 items)
- Walking, running and jumping (24 items).

Items were selected to represent motor functions typically performed by children without motor impairments by 5 years of age. Each item is scored on a 4-point Likert scale (ie, 0 = cannot do; 1 = initiates [<10% of the task]; 2 = partially completes [10% to <100% of the task]; 3 = task completion). The score for each dimension is expressed as a raw score and a percent score, which is the percentage of the maximum score for that dimension. Total raw score is obtained by adding the raw score from each dimension. Total percentage score is obtained by adding the percentage scores for each dimension and dividing the sum by the total number of dimensions. Therefore, each dimension contributes equally to the total score. The total raw score weights each item, not each dimension, equally.

GMFCS-E&R is a 5 level classification system for specific age ranges consisting of Levels I to V based on self-initiated movement, with emphasis on sitting, transfers, and mobility. The distinctions between levels are based on functional limitations, the need for assistive mobility devices, and to a much lesser extent, quality of movement, and are designed to be meaningful in daily life. Level I represents high functioning; Level V represents low functioning.

Pompe Pediatric Evaluation of Disability Inventory

A disease-specific version of PEDI was developed to assess functional capabilities and performance in children with Pompe disease from 2 months through adolescence. The Pompe-PEDI is comprised of a Functional Skills Scale and Caregiver Assistance Scale; both scales have three domains: Self Care, Mobility, and Social Function. The Pompe-PEDI includes all items from the original PEDI, as well as additional items in the Functional Skills Mobility and Self-Care

domains to reflect clinically relevant functional skills for children with Pompe disease. Norm-based scoring was developed for these new items and scoring algorithms for the PEDI have been adjusted to reflect the additional normative data collected for the Pompe-PEDI.

A trained assessor will administer the Pompe-PEDI, Functional Skills Scale: Mobility Domain to the patient or patient's legal guardian. This domain was selected to measure change in mobility secondary to changes in muscle strength; the domain consists of 160 mobility items that a patient or legal guardian reports if the patient is capable or unable of performing. An increase in raw score of 1 point indicates the acquisition of 1 new skill. Test administration requires approximately 15 minutes. The Pompe-PEDI will be centrally scored. Results are reported as raw score, normative standard score (with standard error) and scaled score (with standard error).

Quick Motor Function Test

QMFT will be used to evaluate changes in motor function concurrently with the GMFM-88.

The QMFT is an observer administered test comprising 16 items specifically difficult for patients with Pompe disease. The items are scored separately on a 5-point ordinal scale (ranging from 0 to 4) with a total score of all items ranging between 0 and 64 points. The test was validated in 91 Pompe patients, aged 5 to 76 years, with different levels of disease severity.

A higher QMFT score represents better outcome. If any of the 16 items comprising QMFT is missing, the total score of the QMFT will be considered as missing. QMFT total score is the sum of all item scores. QMFT percentage score is the QMFT total score divided by the maximum score of 64.

Echocardiography

Two-dimensional and M-mode ECHO will be performed and a specified medium (eg, videotape or digital) will be sent to the core central cardiology laboratory for interpretation. A central cardiologist will review all ECHO. This person will be blinded to the patient and study time point. The primary cardiac outcome assessments (measured and derived by an external vendor Biomedical Systems) to be recorded using off-line review include: LVMI, LVM Z-score, left ventricle long axis, cross sectional area, end diastolic volume, end systolic volume, internal diameter, Septal wall diameter, Posterior wall diameter, Ejection Fraction, Left Ventricle sphericity, Left Ventricle thickness:dimension ratio, and Left Ventricle mass:volume ratio. M-mode parameters include: Left Ventricle Internal Dimension, Posterior Wall, Left Ventricle Internal Dimension, and Shortening Fraction. Systolic, Diastolic, and mean blood pressure will be determined. The following Tricuspid Valve/Mitral Valve parameters will also be assessed: Right Ventricular Pressure (by TR jet), TR gradient, Mitral Valve peak E, Mitral Valve peak A, E:A Ratio, and Mitral Valve deceleration time.

Eyelid position measurements

Study participants will have images taken of their eyes while wearing a pair of empty eyeglass frames with rulers attached as a standardized measurement tool at the time points specified in

Protocol Amendment 03 Version 1 Section 1.2. The following eyelid position measurements will be performed by the central reader:

- IPFD,
- MRD-1,
- MPD.

Creatine kinase

CK measurements will come from the central lab, including both total CK and CK with MB fraction.

Composite Score Constructed Considering 3 Domains: GMFM-88 and GMFCS-E&R, Ptosis, and Respiratory Function

The exploratory composite score will be constructed considering 3 domains: GMFM-88 and GMFCS-E&R, ptosis, and respiratory function (measured by the use of respiratory device). Within each domain, the change from baseline to Week 25 will be classified into improvement, unchanged, and worsening ([Appendix A](#)), and then receives a domain score which is determined by the baseline status and the change category according to [Table 1](#). The composite score is the sum of the 3 domain scores.

Table 1- Composite Score Constructed Considering 3 Domains: GMFM-88 and GMFCS-E&R, Ptosis, and Respiratory Function

Domain	Population	Change from Baseline		
		Improvement	Unchanged	Worsening
Respiratory	Suboptimal clinical response/decline ^a	2	1	0
	No suboptimal clinical response/decline	1	0	-1
Motor skills	Suboptimal clinical response/decline ^b	2	1	0
	No suboptimal clinical response/decline	1	0	-1
Ptosis	Suboptimal clinical response ^c	2	1	0
	No suboptimal clinical response	1	0	-1

- a. Suboptimal clinical response is documented sustained decline in percent predicted FVC $\geq 15\%$ or new onset of non-invasive ventilator assistance (acquired for at least 4 weeks prior to study enrollment). If a patient is not old enough to perform PFT properly, assign a score of 0. Clinical decline is new development or worsening of respiratory failure requiring the use or increased use of ventilatory assistance (invasive or non-invasive). Ventilatory assistance must have been required for at least 4 weeks prior to study enrollment,
- b. Suboptimal clinical response is documented worsening of muscle strength demonstrated by a developmental plateau or decrease in GMFM-88 Total Score and/or in scaled scores of Pompe-PEDI scale or in other motor scale and/or clinical developmental evaluation tools. Use GMFM-88 only if the patient entered the cohort due to suboptimal clinical response on Pompe PEDI. Clinical decline for patients ≤ 2 years of age at study entry, is failure to acquire at least 2 new age appropriate gross motor milestones at least 6 months prior to study enrollment; for patients > 2 years of age at study entry, documented worsening of muscle weakness.
- c. Suboptimal clinical response is new onset of ptosis.

If a patient does not have any suboptimal response/decline at baseline for a domain (respiratory, motor skills, or ptosis), a score of 1, 0, or -1 is assigned if a patient improves, remains the same, or declines, respectively, with the exception of improvement for ptosis (which is not possible). Otherwise, if a patient has a suboptimal clinical response/decline at baseline for a domain (respiratory, motor skills, or ptosis), a score of 2, 1, or 0 is assigned if a patient improves, remains the same, or declines. It is under the rationale that stopping a declining trend shall be credited with a higher score.

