	
• Quick Motor Function Test [QMFT]• Echocardiography (ECHO) endpoints: left ventricular mass index (LVMI) and left ventricular mass (LVM) Z-score• Eyelid position measurements: Interpalpebral fissure distance (IPFD), margin reflex distance (MRD-1), margin pupil distance (MPD)• Creatine kinase (CK) 
Other endpoint(s):
 
Pharmacogenetics:
 
• [REDACTED]• [REDACTED]• Optional stored DNA 
Pharmacodynamics:
 
• Urinary Hex4 and [REDACTED]• Muscle biopsy (optional) 
Tertiary endpoints:
 
• 6-minute walk test (6MWT) distance walked in patients who are able to ambulate at least 40 meters (approximately 130 feet) without stopping and without an assistive device• Pulmonary function testing (PFT) endpoints: percent predicted forced vital capacity (FVC), maximal inspiratory pressure (MIP) and maximal expiratory pressure (MEP) in patients who can reliably undergo testing and/or who are not invasively ventilated• Hours of ventilator use/day (Ventilator use diary)• PedsQL Generic Core Scale (≥ 24 months of age)• PedsQL Pediatric Pain Questionnaire (> 5 years of age)• Pain visual analog scale (VAS)• Bayley-III (1-42 months of age or in case the developmental level of an individual patient is below the level required for the Leiter-3 Scale assessment)• Leiter-3 (≥ 42 months of age)• Hearing Testing• Motor Skills Checklist

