9.3.3.3 Ventilator use diary

The Investigator will provide a respiratory diary to the patient (and/or the patient's parent[s]/legal guardian[s]) to record the daily use (if any) of mechanical ventilation (including both invasive and non-invasive) at daytime and nighttime. The date the patient first became dependent on invasive ventilator, as well as the reasons for first ventilator use will be collected and results will be recorded in the e-CRF. If the patient requires mechanical invasive or non-invasive ventilator support during the study, the start date, stop date, and reasons for each episode of continuous mechanical ventilator support will be collected. Invasive ventilation is defined as mechanical ventilatory support applied with the use of an endotracheal tube or tracheostomy, and non-invasive ventilation is defined as ventilatory support applied without the use of an endotracheal tube, ie, no invasion of the airway (39). On a biweekly basis, the periods of ventilator use/day (daytime, nighttime, both) will be reported by the Investigator based on the ventilator use diary and data recorded until (1) ventilator support is no longer needed; (2) patient death; or (3) end of study (whichever occurs first) . The date and reason that ventilator use is no longer needed will be recorded. The daily ventilator use diary is only required to be completed for patients using ventilator support.

If the patient requires any invasive or non-invasive mechanical ventilation (excluding planned ventilatory support less than 3 days duration for a planned surgical procedure), the Investigator will describe the events leading up to the mechanical ventilation using the ventilator use form/log in the e-CRF. Refer to [Section 10.4.1.2](#), [Section 10.4.2](#) and [Section 10.4.3](#) for details regarding recording and reporting events of new invasive ventilatory support (excluding planned ventilatory support less than 3 days duration for a planned surgical procedure).

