FVC will be reported in absolute value in liters. The FVC (% predicted) value is defined as $100^* (\text{actual FVC measurement}/\text{predicted value of FVC})$. The Quanjer GLI-2012 regression equations and lookup tables (1) are used to calculate predicted values of FVC. Predicted values of FVC are functions of sex, age in years (3-95 years), height in cm, and ethnic group (Whites, African Americans, South East Asians, North East Asians and for Other ethnic groups or people of mixed descent). FVC is predicted according to the following equation:

$$M = \exp(a_0 + a_1 \cdot \ln(\text{Height}) + a_2 \cdot \ln(\text{Age}) + a_3 \cdot \text{black} + a_4 \cdot \text{NEAsia} + a_5 \cdot \text{SEAsia} + a_6 \cdot \text{Other} + \text{Mspline})$$

Where

black = 1 if a subject is African American, otherwise = 0

NEAsia = 1 if a subject is from North East Asia, otherwise = 0

SEAsia = 1 if a subject is from South East Asia, otherwise = 0

Other = 1 if subject is 'other ethnic group' or mixed ethnicity, otherwise = 0

Coefficients a(n) depend on sex and are given by lookup table

Mspline is age-varying coefficients, given by lookup table for each type of sex

For the analysis purpose, the age will be calculated based on (assessment date - birth date + 1)/365.25. Height will be based on the most recent valid value at or prior to the assessment date.

The percent predicted values for MIP and MEP will be calculated (6, 7). The normal reference values used for percent predicted calculation will be dependent on each patient's age, gender, and weight (Table 3). For each patient, the same equations used for the baseline will be used to calculate the predicted values (eg, if a patient started at ≤ 17 years of age and turns 18 during the study, he/she will still use the pediatric formula after turning to 18). For analysis purposes, the age will be calculated based on (assessment date - birth date + 1)/365.25. Weight for age < 18 will be based on the most recent valid value at or prior to the assessment date. The percent predicted value is defined as $(\text{absolute measurement}/\text{normal reference value}) * 100$. Since the reference

values will be available only for patients of age 7 years or older, the percent predicted MIP and MEP will not be derived for patients aged <7.

Table 3 - Reference equations for predicted value of MEP and MIP

Test/Age at baseline	Male	Female
MEP		
≥18 years old (6)	174 – 0.83 * age	131 – 0.86 * age

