7–17 years old (7)	35 + 5.5 * age	24 + 4.8 * age
MIP		
≥18 years old (6)	120 – 0.41 * age	108 – 0.61 * age
7–17 years old (7)	44.5 + 0.75 * weight	40 + 0.57 * weight

Age in years; weight in kg.

All PFTs will be reported centrally from Biomedical Systems (BMS) following pulmonary software specification and user requirement (2).

Ventilator use diary

The Investigator will provide a respiratory diary to the patient (and/or the patient's parent[s]/legal guardian[s]) to record the daily use (if any) of mechanical ventilation (including both invasive and non-invasive) at daytime and nighttime. The date the patient first became dependent on invasive ventilator, as well as the reasons for first ventilator use will be collected and results will be recorded in the e-CRF. If the patient requires mechanical invasive or non-invasive ventilator support during the study, the start date, stop date, and reasons for each episode of continuous mechanical ventilator support will be collected. Invasive ventilation is defined as mechanical ventilatory support applied with the use of an endotracheal tube or tracheostomy, and noninvasive ventilation is defined as ventilatory support applied without the use of an endotracheal tube, i.e., no invasion of the airway. On a bi-weekly basis, the average number of hours of ventilator use/day will be calculated by the Investigator based on the ventilator use diary and data recorded until (1) ventilator support is no longer needed; (2) patient death; or (3) end of study (whichever occurs first). The date and reason that ventilator use is no longer needed will be recorded. The daily ventilator use diary is only required to be completed for patients using ventilator support.

If the patient requires any invasive or non-invasive mechanical ventilation (excluding planned ventilatory support less than 3 days duration for a planned surgical procedure), the Investigator will describe the events leading up to the mechanical ventilation using the ventilator use form/log in the e-CRF.

PedsQL Generic Core Scale questionnaire

The PedsQL Generic Core Scales is a general HRQOL tool. If patients are unable to complete this assessment, a parent proxy form will be used. During the treatment period, the assessment will be completed before IMP infusion if possible, and the patients will continue on the age-

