7 LIST OF APPENDICES

[Appendix A](#): Classification of changes (including improvement, unchanged or worsening) from baseline to Week 25 for the 3 domains comprising the composite score

[Appendix B](#) Potentially clinically significant abnormalities (PCSA) criteria

Appendix A Classification of changes (including improvement, unchanged or worsening) from baseline to Week 25 for the 3 domains comprising the composite score (9).

Parameter	Baseline	Week 25		
		Improvement	Unchanged	Worsening
Respiratory	No use of any ventilation assistance	NA	No use of any ventilation assistance	Use of any ventilation assistance
	Use non-invasive ventilation assistance during daytime only or nighttime only	No use of any ventilation assistance	Use non-invasive ventilation assistance during daytime only or nighttime only	Use non-invasive ventilation assistance during both daytime and nighttime Use invasive ventilation assistance
	Use non-invasive ventilation assistance during both daytime and nighttime	No use of any ventilation assistance Use non-invasive ventilation assistance during daytime only or nighttime only	Use non-invasive ventilation assistance during both daytime and nighttime	Use invasive ventilation assistance
	Use invasive ventilation assistance during daytime only or nighttime only	No use of any ventilation assistance Use non-invasive ventilation assistance	Use invasive ventilation assistance during daytime only or nighttime only	Use invasive ventilation assistance during both daytime and nighttime
	Use invasive ventilation assistance during both daytime and nighttime	No use of any ventilation assistance Use non-invasive ventilation assistance Use invasive ventilation assistance <24 hrs/day	Use invasive ventilation assistance during both daytime and nighttime	NA
Motor Skills: GMFM-88 Total Score ^a	Level I Walker	Total Score increase ≥ 3.22	$-3.22 < \text{Total Score change} < 3.22$	Total Score decrease ≥ 3.22
	Level II Supported walker	Total Score increase ≥ 2.76	$-2.76 < \text{Total Score change} < 2.76$	Total Score decrease ≥ 2.76
	Level III Supported stander	Total Score increase ≥ 1.41	$-1.41 < \text{Total Score change} < 1.41$	Total Score decrease ≥ 1.41
	Level IV Sitter	Total Score increase ≥ 1.65	$-1.65 < \text{Total Score change} < 1.65$	Total Score decrease ≥ 1.65
	Level V Restricted antigravity movement	Total Score increase ≥ 0.8	$-0.8 < \text{Total Score change} < 0.8$	Total Score decrease ≥ 0.8

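### Composite score: SAP Table 1 footnote a assigns 0 to children too young for lung function tests although respiratory change is scored from ventilation status; three smaller scoring rules also need repair

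*SAP*

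**What the plan says.** SAP 2.1.6 builds the composite from motor skills, ptosis and "respiratory function (measured by the use of respiratory device"). Appendix A sorts each domain's change to Week 25 into Improvement, Unchanged or Worsening, and every respiratory cell is a ventilation state. Table 1 then scores 2, 1 or 0 if the child had a sub-optimal response or decline in that domain before entry, and 1, 0 or -1 if not. The reason given is that "stopping a declining trend shall be credited with a higher score".

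Footnote a, attached to the respiratory decline row, allows entry to that row by FVC decline or by ventilation. It then adds: "If a patient is not old enough to perform PFT properly, assign a score of 0".

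On the smaller points:

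- **Ventilation cells.** For a child on invasive ventilation day and night at baseline, Improvement in Appendix A includes "Use invasive ventilation assistance <24 hrs/day", while Unchanged is invasive ventilation in both periods. Protocol 9.3.3.3 says "the periods of ventilator use/day (daytime, nighttime, both) will be reported by the Investigator based on the ventilator use diary"; SAP 2.1.9 says "the average number of hours of ventilator use/day will be calculated by the Investigator based on the ventilator use diary". The protocol summary still lists "Hours of ventilator use/day (Ventilator use diary") as a tertiary endpoint.
- **Motor rows.** Appendix A labels its rows Walker, Supported walker, Supported stander, Sitter and Restricted antigravity movement. These are the Pompe Functional Classification names of protocol 9.3.3.9. The Appendix A footnote calls the levels GMFCS.
- **Missing Week 25.** SAP 2.5.2 substitutes Week 13. Table 5 in SAP 2.5.4 files efficacy visits by actual date and keeps the value nearest the target day.

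**The concern.** Change in the respiratory domain can be classified at any age, because it rests on ventilation. A child too young for spirometry can still be placed in the decline row by ventilation, and Table 1 then gives a proper score. The footnote sentence appears to overrule that score with 0. In the decline row, 0 is what a child who worsens receives, so a halted or reversed decline would be recorded as worsening. That runs against the SAP's own rationale.

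At stake are the reported scores and the arm difference in the endpoint that SAP 3 treats as the only hypothesis test. With about 5 children per arm, one score is visible in the mean. The smaller defects can each shift a score by one point, or leave two programmers with different scores from the same data.

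**Working it through.** The plan gives no sample size calculation or expected score, so there is no figure to reproduce. The check applies the scoring rules as written.

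**Inputs.** Table 1 scores and footnotes (SAP 2.1.6); change cells and motor thresholds (Appendix A); at least 10 children randomized 1:1 in Cohort 3, hence 5 per arm at the minimum (SAP 1.1); visit windows (SAP Table 5).

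**Footnote a.** A percent predicted FVC is not available at every age: "Predicted values of FVC are functions of sex, age in years (3-95 years"). The footnote gives no age of its own. A child who cannot provide FVC reaches the decline row only by ventilation. Effect of a literal 0 = 0 minus the Table 1 score; arm-mean effect = that difference / 5.

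| Row, change | Table 1 | Effect of flat 0 | Arm mean |
|---|---|---|---|
| Decline, improved | 2 | -2 | -0.4 |
| Decline, unchanged | 1 | -1 | -0.2 |
| Decline, worsened | 0 | 0 | 0 |
| No decline, unchanged | 0 | 0 | 0 |
| No decline, worsened | -1 | +1 | +0.2 |

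The last two lines apply only if the sentence reaches beyond the row that carries its marker. Two milder readings exist. If 0 means only that the FVC criterion is unmet, ventilation still sets the row and nothing changes. If it moves the child to the no-decline row, each decline-row child loses exactly 1 point.

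Illustration with invented composite scores, 5 v 5, gender strata ignored (252 allocations): 2, 2, 3, 1, 2 against 0, 0, 1, 0, -1 gives a difference of 2.0 and p = 4/252 = 0.016. Lowering the 3 to 1, a loss of 2 points, gives 1.6 and p = 6/252 = 0.024.

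**Ventilation cells.** Invasive support for 20 hours spread over day and night (assumed value) is under 24 hours and also in both periods. It fits Improvement and Unchanged: 2 or 1 in the decline row, 1 or 0 in the other.

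**Motor rows.** GMFCS Level III in protocol 9.2.2.1 is walking with a hand-held device, whereas the Level III row in Appendix A reads Supported stander. Such a child has threshold 1.41 as GMFCS III, but 2.76 if counted as a Supported walker (assumed mapping). GMFM-88 changes from 1.41 to below 2.76, in either direction, are classified differently. A gain of 2.0 is Improvement under one key and Unchanged under the other: 1 point, or 0.2 on the arm mean.

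**Missing Week 25.** The Week 13 window ends on Day 85 + 41 = 126; the Week 25 window opens on Day 169 - 42 = 127. Two-weekly ventilator and eyelid records (protocol 10.1.2.4) at Weeks 15 and 17 fall on Days 99 and 113, inside the Week 13 window. If a Day 85 value exists, it is nearer the target and they are passed over. The Week 25-type assessments done at early discontinuation (protocol 10.1.7) are treated the same way if they fall before Day 127. An unventilated child with no prior respiratory decline, ventilated from Day 99 and without data from Day 127, scores 0 instead of -1: again 0.2.

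**The case against.** The composite is exploratory, its p-values are references only (SAP 2.4.8), and the number of children affected may be zero. This limits the consequence but does not make the rules right. The other arguments need separate answers.

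- **The domain does use lung function.** This is correct for the baseline row, where FVC decline is one route in. A reader might infer that the domain never needs PFT; that is too broad. Only the change classification is free of it.
- **The 0 may be meant harmlessly**, as FVC criterion not met. That is possible, and the text does not decide it. The ambiguity itself needs removing.
- **The hours cell is a version mismatch.** The SAP cites a protocol dated 27 July 2018, and the diary text was revised in the 2020 amendment. This explains periods against hours, but not the overlap of the two cells. Few Cohort 3 children would reach the cell, because respiratory entry there is by FVC decline or non-invasive ventilation; it is likelier in Cohorts 1 and 2, to which SAP 1.6 extended the score.
- **The Appendix A footnote is explicit about GMFCS.** It is, and a labelling slip would explain the mismatch. A reader might infer that wrong thresholds will be applied. The documents do not show this, nor which key is right.
- **Follow-up safeguards exist.** Children who stop treatment are to be followed as scheduled (protocol summary), and a missed efficacy visit is made up later (protocol 10.1.6). Weeks 19 to 23 already fall in the Week 25 window, so it would be wrong to say that all records between Weeks 13 and 25 are ignored. What remains is the child without data from Day 127 on.

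**Conclusion.** The concern stands in this limited form and should be fixed. Read literally, footnote a gives a too-young child placed in the decline row by ventilation the Worsening value whatever happened. The error is 1 or 2 points, or 0.2 or 0.4 on a mean of 5. This assumes the minimum cohort size and the literal reading. The ventilation overlap, the motor labels and the Week 13 selection each put about 1 point (0.2) at risk for an affected child; the motor example also assumes the mapping stated above.

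Three stronger conclusions are not supported:

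- **An invalid or slanted test.** The rules apply alike in both arms, so the re-randomization test remains valid under the null.
- **An error in scoring a missing domain baseline as 0.** That rule is pre-specified in SAP 2.5.2 and does not contradict Table 1.
- **A need to score early loss as Worsening, or death as a fixed -3.** The first would take an unchanged motor-only decliner from 1 + 0 + 0 = 1 to 0 - 1 - 1 = -2 without observed worsening. The second would tie with a surviving Stage 1 child who entered on cardiac criteria alone and worsened in all three domains.

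**What to change.** 1. Delete the PFT-age sentence from footnote a, or restrict it to saying that the FVC criterion is not assessable. Score respiratory change from ventilation status at every age.
2. In Appendix A, replace the under-24-hours entry with invasive ventilation in daytime only or nighttime only, as in the neighbouring rows.
3. Check the source of the motor thresholds and make the row labels and the footnote name one classification.
4. If no value falls in the Week 25 window, carry forward for each domain the last post-baseline value before Day 127, including the discontinuation visit and the two-weekly ventilator and eyelid records.

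The cost is SAP text and derivation code, plus one look at the threshold source. No data collection changes.
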